5.6. Accountability of Study Drug

The investigator and investigational site staff are responsible for maintaining an accurate inventory and accounting of study drug. A record of all vials of study drug received and administered will be maintained on an investigational drug inventory form provided by the Sponsor or an equivalent drug inventory form. The following information will be recorded:

- Date, quantity, and lot number(s) of study drug received
- Date, quantity, and lot number(s) of study drug dispensed from the pharmacy per patient
- Date, quantity, and lot number(s) of study drug administered to each patient
- Date, quantity, and lot number(s) of study drug destroyed (if prepared and dispensed, but not administered for any reason, the study drug may not be returned to inventory)
- Date, quantity, and lot number(s) of study drug returned to sponsor, if applicable

Each shipment of study drug will contain an invoice describing the amount of drug shipped to the investigational site. The information on the invoice will be verified against the actual amount received, after which the investigator or designee will place the invoice in the investigator's file. The Sponsor's monitor will reconcile the information on the investigational drug inventory form with the actual amount of study drug remaining at each site on a routine basis. At the conclusion of the study, the monitor will either package and ship all unused vials of study drug back to Sponsor for destruction or document the destruction, in accordance with local regulations and institutional policy. Following use, empty vials of study drug may be destroyed according to local regulatory and environmental requirements. A record of any such destruction will be placed in the investigator's file.

6. SCHEDULE OF ASSESSMENTS

6.1. COVID-19 Public Health Emergency Impact on Protocol Assessments

During study conduct, challenges may arise, for example, from quarantines, site closures, travel limitations, interruptions to the supply chain for the investigational product, or other considerations if site personnel or study participants become infected with COVID-19. These challenges may lead to difficulties in meeting protocol-specified procedures, including administering the study drug or adhering to protocol-mandated visits and laboratory/diagnostic testing. During the course of study conduct, protocol modifications may be required, and there may be unavoidable protocol deviations due to COVID-19 illness and/or COVID-19 public health control measures. In such case, these incidences should be documented in the study case report form(s).

Since study participants may potentially not be able to come to the investigational site for protocol specified visits, alternative methods for safety and efficacy assessments (e.g., phone contact, virtual visit, telemedicine, visiting nurse to patient's residence, alternative location for assessment, including local labs or imaging centers) could be implemented when necessary and feasible, and would be sufficient to assure the safety of study participants.

6.2. Schedule of Assessments

The study schedule of events can be found in Table 4. Detailed information of study assessments is provided in Section 7.

Table 4: Schedule of Assessments

Evaluation / Procedure Visit Window	Screening (D-28 to 0)	Treatment	End of Treatment Visit (EOT) ¹³	Survival Follow-Up Every 3 months after EOT ¹⁵
		Evaluations/Procedures +/-2 days Seribantumab Dosing +2 days	± 3 days	± 1 month
Informed consent	X			
Medical, surgical, malignancy history	X			
Archived tumor tissue or fresh biopsy	X		X ¹⁴	
Urine or serum pregnancy test	X	Every 28 days	X	
Physical Exam and ECOG PS ¹	X	Weekly during C1, then at W1 of every Cycle thereafter	X	
Vital signs	X ⁸	X	X	
CBC	X ^{2,8}	Weekly during C1, then every 14 days starting C2W1 then every 28 days starting after 1 year on treatment	X	
Serum chemistry	X ^{3,8}		X	
Blood sample(s) for PK ⁴		C1W1, C1W3, C2W1, C2W3, C3W1, C3W3, C4W1, C5W1, C6W1, and then every even Cycle beginning with C8W1		
12-lead ECG	X ⁵		X ⁵	
Serum for anti-seribantumab immunogenicity ⁶		C1W1, C1W3, C2W1, C2W3, C3W1 and C3W3, C4W1, C5W1, C6W1, and then every even Cycle beginning with C8W1	X ⁶	
Whole blood for cfDNA ⁷		C1W1 and C2W1	X	
Concomitant meds ⁸	X	X	X	
Seribantumab dosing ⁹		X		
AE/SAE assessment and reporting ¹⁰		X		
Quality of Life Questionnaire (EORTC QLQ-C30)		C1W1, and at W1 of every other Cycle ¹⁶	X	
Disease evaluation	X ¹¹	Week 6, Week 12, Week 18, Week 24; then every 8 weeks (through Week 48); then every 12 weeks (beginning at Week 60)	X ¹²	
Overall Survival Reporting ¹⁵				X

AE = adverse event; ALT = alanine aminotransferase; AST = aspartate aminotransferase; BUN = blood urea nitrogen, C = cycle; CBC = complete blood count; cfDNA = cell free DNA; CT = computerized tomography; ECG = electrocardiogram; ECOG PS = Eastern Cooperative Oncology Group performance status; EOI = end of infusion; EORTC QLQ-C30 = European Organization for Research and Treatment of Cancer Quality of Life

Questionnaire-Core 30; EOT = end of treatment; GI = gastrointestinal; HEENT = head, eyes, ears, nose, and throat; Ig = immunoglobulin; LDH = lactate dehydrogenase; MRI = magnetic resonance imaging; NSCLC = non-small cell lung cancer; RBC = red blood cell; RECIST = Response Evaluation Criteria in Solid Tumors; SAE = serious adverse event; W = week; WBC = white blood cell

- ¹ Review of systems: HEENT, extremities, GI/abdomen, lymph nodes, musculoskeletal, respiratory/pulmonary, and skin, body weight, and height during Screening. Symptom-directed physical and neurological examinations, including measurement of weight, may be performed at other time points. After screening, physical exams should occur weekly during Cycle 1 and at Week 1 of every cycle thereafter.
- ² Hemoglobin, hematocrit, RBC count, WBC count with differential (neutrophils [count and percent] and lymphocytes, monocytes, eosinophils, basophils [percent], and platelet count). Samples collected for Screening may be used for C1W1 if collection occurs within 2 days of the C1W1 visit. Ad hoc samples may be requested by the Sponsor or at the investigator's discretion.
- ³ Serum or plasma chemistries (non-fasting), including alkaline phosphatase, albumin, ALT, AST, blood urea nitrogen (BUN), cholesterol, creatinine, glucose, LDH, uric acid, total and direct bilirubin, total protein, sodium, potassium, calcium, chloride, bicarbonate, magnesium and phosphate. Samples collected for Screening may be used for C1W1 if collection occurs within 2 days of the C1W1 visit. Ad hoc samples may be requested by the Sponsor or at the investigator's discretion.
- ⁴ Seribantumab PK sampling: At C1W1 sampling should occur immediately prior to dosing, at the end of infusion (EOI) and 1 hour after EOI. At C1W3, C2W1, C2W3, C3W1, C3W3, C4W1, C5W1, C6W1, and then every even Cycle beginning with C8W1: Samples should be collected immediately prior to each dose and at the EOI. Sampling should occur within 15 minutes of starting or completing the seribantumab infusion. Ad hoc PK samples may be requested by the Sponsor.
- ⁵ Screening electrocardiogram (ECG) should be performed in triplicate. End of Treatment (EOT) ECG reading should be repeated only if the initial reading at the EOT visit showed treatment emergent abnormalities. Ad hoc ECGs may be requested by the Sponsor.
- ⁶ Anti-seribantumab immunogenicity samples should be collected prior to dosing at scheduled time points. Should a patient experience an infusion reaction on study, an anti-seribantumab antibody assay will be taken within 24 hours of the event. For patients who experience a grade 3 or 4 infusion reaction, an anti-seribantumab antibody titer will be taken as close to the onset of the infusion reaction as possible, upon resolution and 28 days (\pm 2 days) following the event.
- ⁷ Whole blood for cfDNA analysis should be obtained prior to treatment on C1W1 and C2W1. Whole blood for cfDNA analysis should be obtained at the EOT visit even if radiographic disease assessment is not performed. Whole blood for cfDNA analysis should only be collected at subsequent visits if it was collected prior to treatment at C1W1.
- ⁸ Performed prior to seribantumab administration.
- ⁹ Seribantumab dosing will consist of weekly 1-h infusions until study treatment discontinuation criteria are met. Seribantumab doses should be administered no less than 7 days apart.
- ¹⁰ All AEs and SAEs are collected and reported from the time of informed consent through the EOT visit or 28 days after last dose, whichever occurs later.
- ¹¹ Baseline Disease Assessment: Radiographic tumor measurements using CT (computerized tomography) or magnetic resonance imaging (MRI) of the chest, abdomen, and pelvis, with additional regions affected by disease as appropriate, and CT or MRI of brain (for patients with suspected brain involvement or a history of brain metastases) within 28 days of seribantumab dosing (first dose). Contrast should be utilized (excluding CT of the chest) unless there is a clear contraindication (e.g., decreased renal function or allergy that cannot be addressed with standard prophylactic treatments). Disease assessments will utilize RECIST v1.1. Disease assessments will occur prior to seribantumab administration on dosing days and occur within a \pm 14-day window. Refer to Section 7.7 for details on confirmation of response.
- ¹² All patients that come off treatment for reasons other than progressive disease will have a disease assessment performed at the EOT visit.
- ¹³ End of Treatment visit should be completed within 4 weeks of the last dose of study drug administration.
- ¹⁴ An optional fresh tumor biopsy will be performed at the time of progression and prior to the completion of the EOT assessments if feasible to evaluate potential patterns of resistance to seribantumab.
- ¹⁵ Every survival follow-up should include collection of any new anti-cancer therapies and procedures taken after EOT visit. Should patients refuse or drop out of survival follow-up, attempts should be made to obtain any death information available via public records.

¹⁶ European Organization for Research and Treatment of Cancer (EORTC) Quality of Life Questionnaire-Core 30 (QLQ-C30) should be conducted prior to dosing at C1W1 and at W1 of every other cycle thereafter, i.e., C3W1, C5W1, etc. The questionnaires should be answered by the patient to the best of his/her ability, preferably prior to learning the results of the radiologic disease assessment. QOLs should only be performed at subsequent visits if they were performed prior to dosing at C1W1.

6.3. Screening and Baseline Visit

All procedures for screening and baseline are outlined in Section 6.2. Patients who screen fail can be rescreened. Rescreened patients will be provided a new patient identification number.

In discussion with the Sponsor, if a patient is identified who does not have access to local NRG1 fusion testing, the Sponsor may offer support for testing of enriched patient population as a pre-screening procedure. Enriched patient population may include patients diagnosed with KRAS wild-type IMA, and KRAS wild-type pancreatic ductal adenocarcinoma (PDAC). Additional tumor types of interest may be added at the Sponsor's discretion. For patients diagnosed with IMA or PDAC who have not been screened for KRAS status, the Sponsor may provide access to KRAS testing under the pre-screening mechanism. The Sponsor may also support testing for patients with other tumor types who have exhausted all other options for treatment. For further descriptions of the clinical and laboratory assessments required, please refer to Section 7 and Section 8, respectively.

6.4. On-Study Visits

Patients who are confirmed to meet all inclusion and exclusion criteria will be assigned to the appropriate treatment cohort based upon prior treatment history. Treatment must be initiated within 7 days of Enrollment and Cohort Assignment.

All on-study procedures and assessments are outlined in Section 6.2.

6.5. End of Treatment Visit

When it is decided that a patient will stop receiving treatment on this study, an End of Treatment visit must be completed within 4 weeks of last dose of study drug and prior to the initiation of any subsequent anticancer therapy. All End of Treatment procedures and assessments are outlined in Section 6.2.

6.6. Survival Follow-up

Survival data will be collected via written communication (e.g., telephone, email, electronic medical record) or clinic visits every 3 months (± 28 days) from the date of last treatment until death, loss to follow-up, withdrawal of consent, or study termination by the Sponsor. In addition, any new anti-cancer therapies and procedures should be collected and documented during every survival follow-up. All survival information will be captured using the electronic data capture (EDC) system. Should patients refuse or drop out of survival follow-up, attempts should be made to obtain any death information via public records whenever possible.

7. CLINICAL PROCEDURES AND ASSESSMENTS

All of the following clinical procedures should be performed in accordance with the schedule of assessments outline in Section 6.2.

7.1. Medical History and Demographics

Demographic information including age, date of birth, race, ethnicity and gender will be collected at the time of Screening.

A medical history will be collected including all pertinent prior medical conditions, surgeries or other medical procedures, allergies, and concomitant medications.

7.2. Adverse Event and Hospitalization Assessment Reporting

Investigators should complete all routine and standard of care assessments to evaluate for toxicity and symptoms of drug-induced AEs. This may include, but is not limited to, verbal reports from the patient and/or caregiver, physical examination and laboratory findings. Adverse events should be collected and reported throughout the course of the study, from the time of informed consent through the end of treatment (EOT) visit or 28 days after the last dose of seribantumab, whichever occurs later, and followed through to resolution as detailed in Section 9.

In addition, information on patient hospitalizations and/or unscheduled hospital visits should also be collected in the eCRF, whether or not associated with an AE.

7.3. Physical Examination and Performance Status Assessment

Physical examination will include a review of systems: head, eyes, ears, nose, and throat, extremities, GI/abdomen, lymph nodes, musculoskeletal, respiratory/pulmonary, and skin, body weight, and height during Screening. Symptom-directed physical and neurological examinations, including measurement of weight, may be performed at other time points. The ECOG performance status will be obtained by the Investigator or his/her designee by questioning the patient about their functional capabilities.

7.4. Vital Signs

Vital signs will be collected at Screening and prior to seribantumab administration at dosing visits and should include resting blood pressure, pulse, respiratory rate, and temperature.

7.5. Electrocardiogram

A 12-lead electrocardiogram (ECG) will include a description of the cardiac rate, rhythm, interval durations, and an overall impression. The corrected QT interval (QTc) should be calculated using the Fridericia method (QTcF).

7.6. Collection of Quality of Life (EORTC QLQ-C30) Questionnaire

The EORTC QLQ-C30 should begin to be implemented for newly enrolled patients when available. Only patients who have completed questionnaires at baseline (prior to dosing at C1W1) should complete subsequent questionnaires at the follow up periods.

7.7. Disease Evaluation

Tumor response will be evaluated by the local radiologist according to the RECIST v1.1 (Eisenhauer et al., 2009) to establish disease progression by computerized tomography (CT) or magnetic resonance imaging (MRI) of chest, abdomen, and pelvis at minimum, and in additional regions such as head, neck, or extremities, as appropriate if disease or symptoms are present. Patients enrolled with a history of central nervous system (CNS) metastases should additionally have a head CT/MRI scan with contrast performed at each tumor assessment. The same method of assessment must be used throughout the study. Please refer to image acquisition guidelines for the requirements for image collection and scanner qualification. Independent retrospective central reviews of all scans may be conducted in addition to review performed by the local radiologist. Investigators should choose target and non-target lesions in accordance with RECIST v1.1 guidelines. Follow-up measurements and overall response should also be in accordance with these guidelines. To be assigned a status of confirmed PR or CR, changes in tumor measurements must be confirmed by repeated assessments that should be performed ≥ 28 days after the criteria for response are first met.

Patients that discontinue study drug administration for reasons other than progressive disease including due to toxicities will continue to receive tumor assessments beginning at weeks 6, 12, 18 and 24 with a ± 2 -week window and subsequently every 8 weeks (± 2 weeks) through Week 48, followed by every 12 weeks (± 2 weeks) beginning at Week 60 until disease progression and evaluated using the RECIST guidelines (version 1.1). Patients will be evaluated until disease progression, initiation of next anti-cancer therapy, death, or withdrawal of consent.

7.7.1. Independent Central Review of Scans

All treatment decisions will be made by the Investigator using local assessments. All images should be submitted to a central imaging facility and may be analyzed centrally by independent reviewers in accordance with the Imaging Charter. Please refer to the image acquisition guidelines for details on how images must be acquired and how scanners must be qualified. In addition, bone scans, x-rays, cytologic data (e.g., relevant cytology reports documenting malignant pleural effusions, bone marrow aspirations, cerebral spinal fluid, etc.), and relevant clinical information including medical photography will be forwarded to the review facility to aid in the tumor response assessment. Full details are listed in the Imaging Charter.

NOTE: Data from the independent review of tumor measurements will not be sent back to investigators.

8. LABORATORY PROCEDURES AND ASSESSMENTS

8.1. Complete Blood Count

The complete blood count will include the following: hemoglobin, hematocrit, platelet count, red blood cell, WBC with differential (neutrophils, lymphocytes, monocytes, eosinophils, basophils, and other cells).

8.2. Serum Chemistry

Serum or plasma chemistry (non-fasting) will include electrolytes (sodium, potassium, calcium, chloride, bicarbonate, magnesium, and phosphate), blood urea nitrogen, serum creatinine, cholesterol, glucose, total and direct bilirubin, AST, ALT, alkaline phosphatase, lactate dehydrogenase, uric acid, total protein, and albumin.

8.3. Urine or Serum Pregnancy Test

A urine or serum pregnancy test will be obtained for all females of childbearing potential. Exempt female patients will include those who have undergone a bilateral oophorectomy or hysterectomy, or those who are menopausal (defined as absence of a menstrual cycle for at least 12 consecutive months). The reason for exemption should be recorded in the medical history.

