- j. Willingness of men and women of reproductive potential to observe conventional and effective birth control for the duration of treatment and for 3 months following study completion.

Notes:

- A postmenopausal woman will be defined as having no menses for 12 months without an alternative medical cause. Male sterility will be defined as only men sterilized surgically. For male patients with a pregnant partner, a condom should be used for contraception. For male patients with a non-pregnant female partner of child-bearing potential and woman of child-bearing potential one of the following birth control methods with a failure rate of less than 1% per year when used consistently and correctly are recommended:
 - Combined estrogen and progestogen containing hormonal contraception associated with inhibition of ovulation given orally, intravaginally, or transdermally
 - Progestogen-only hormonal contraception associated with inhibition of ovulation given orally, by injection, or by implant
 - Intrauterine device
 - Intrauterine hormone-releasing system
 - Bilateral tubal occlusion/ligation
 - Vasectomized partner
 - Sexual abstinence
 - Sexual abstinence is considered a highly effective method only if defined as refraining from heterosexual intercourse during the entire period of risk associated with the study treatments. The reliability of sexual abstinence needs to be evaluated in relation to the duration of the clinical study and the preferred and usual lifestyle of the patient.
- Birth control methods unacceptable for this clinical study are:
 - Periodic abstinence (calendar, symptothermal, or post-ovulation methods)
 - Withdrawal (coitus interruptus)
 - Spermicide only
 - Lactational amenorrhea method

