4.2. Exclusion Criteria

Patients who meet any of the following criteria will be excluded from participation in this study:

- k. Additional alterations in known oncogenes other than NRG1 fusion that could confer resistance to seribantumab monotherapy treatment, including alterations for which there are approved targeted therapies. Genomic testing reports from locally obtained molecular testing documenting NRG1 fusion must be submitted to the Sponsor for review during the screening period
- l. Life expectancy < 3 months
- m. Pregnant or lactating
- n. Prior treatment with pan-ERBB or any ERBB/HER2/HER3 directed therapy (exclusion for Cohort 1 only)
- o. Symptomatic or untreated brain metastases

- *Note: Patients with asymptomatic brain metastases treated with radiation or surgery and without evidence of progression by imaging at screening are eligible to participate in the study, including those on a stable [i.e., same dose for ≥ 2 weeks] low-dose corticosteroid regimen. Refer to Section 5.5.*
- *Note: Patients with history of brain metastases or if clinically indicated will require brain imaging at baseline and subsequent serial scans if brain metastases are present at baseline.*
- p. Received other systemic anticancer therapy (investigational or standard chemotherapy, immunotherapy, or targeted therapy) within 28 days prior to planned start of seribantumab or 5 half-lives, whichever is shorter
- q. Prior to initiation of seribantumab treatment, patients must have recovered from clinically significant toxicities from prior anticancer or investigational therapy or acute radiation toxicities
- r. Any other active malignancy requiring systemic therapy
- s. Known hypersensitivity to any of the components of seribantumab or previous National Cancer Institute (NCI) Common Terminology Criteria for Adverse Events (CTCAE) grade 3 or higher hypersensitivity reactions to fully human monoclonal antibodies
- t. Clinically significant cardiac disease, including symptomatic congestive heart failure, unstable angina, acute myocardial infarction within 6 months of planned first dose, or unstable cardiac arrhythmia requiring therapy (including torsades de pointes), or prolongation of the QT interval corrected for heart rate (QTcF) > 470 ms on at least 2 of 3 consecutive ECGs, and mean QTcF > 470 ms on all three ECGs during screening. Correction of suspected drug-induced QTcF prolongation may be attempted at the investigator's discretion if considered clinically safe

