5.2.3. Seribantumab Dosing, Preparation and Administration

5.2.3.1. Seribantumab Dosing

Patients enrolled will initiate treatment with seribantumab 3,000 mg 1-h IV once weekly until patients meet one or more protocol-specific treatment discontinuation criteria.

In the setting of weekly dosing, it is expected that during the course of treatment patients may need to miss doses for non-adverse event related reasons; for example, due to weather conditions making travel to the clinic difficult, due to holidays or vacation, etc. After the patient has been on treatment for at least 6 cycles, occasional missed doses during weekly dosing for non-adverse event related reasons would not constitute protocol deviations. No more than one missed dose in

an 8 week period is permissible. A discussion should be held with the Sponsor if the patient falls below 80% compliance with the assigned dosing regimen.

Dose modifications (Section 5.3) and/or treatment interruptions (Section 5.2.4.3) to manage treatment related toxicities are permitted during weekly dosing.

After 12 months of weekly dosing, patients who have tumor response (CR or PR) per RECIST v1.1 may transition from treatment with seribantumab 3,000 mg once every week to once every 2 weeks (Q2W) after discussion with and approval from the Sponsor.

For previous seribantumab dosing schedules, see [Appendix A](#).

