5.5. Concomitant and Prohibited Therapies

Standard supportive medications may be used in accordance with institutional guidelines and Investigator discretion. These may include hematopoietic growth factors to treat neutropenia, thrombocytopenia or anemia in accordance with American Society of Clinical Oncology (ASCO) Guidelines (but not for prophylaxis in Cycle 1), transfusions, anti-emetics, anti-diarrheals, antibiotics, antipyretics, and corticosteroids (up to 10 mg per day prednisone or equivalent, unless a compelling clinical rationale for a higher dose is articulated by the Investigator and approved by the Sponsor; permitted corticosteroid uses include topical/cutaneous, ophthalmic, nasal and inhalational steroids, as well as short courses to treat asthma, chronic obstructive pulmonary disease, or other non-cancer related conditions).

All concomitant medications, including transfusions of blood products, will be recorded on the appropriate page of the case report form. Concomitant therapy (non-investigational products) includes any prescription medication, over-the-counter preparation, herbal therapy, or radiotherapy used by a patient between the 28 days preceding study treatment initiation and the study treatment discontinuation visit. After the End of Treatment Visit, only anti-cancer therapies will be collected in addition to survival information.

The following therapies are not permitted while on study treatment:

- Other anti-neoplastic therapy, including cytotoxics, targeted agents, endocrine therapy, or other antibodies (patients who have been on gonadotropin-releasing hormone analogues for more than 90 days prior to study entry may continue while on study)

- Any other investigational therapy

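### The pregnancy-test exemption in Protocol 8.3 uses a looser definition of menopause than 4.1(j), so a literal reading leaves some possibly fertile women untested

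*Protocol*

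**What the plan says.** Protocol 8.3 opens with a general rule: "A urine or serum pregnancy test will be obtained for all females of childbearing potential". It then lists who is exempt: women after bilateral oophorectomy or hysterectomy, and "those who are menopausal (defined as absence of a menstrual cycle for at least 12 consecutive months". It adds one administrative safeguard: "The reason for exemption should be recorded in the medical history".

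The notes to inclusion criterion 4.1(j), which deals with contraception, define the same status differently: "A postmenopausal woman will be defined as having no menses for 12 months without an alternative medical cause".

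Table 4 (Protocol 6.2) schedules the test at screening, every 28 days on treatment, and at End of Treatment. Its footnotes add nothing about menopausal status.

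The test supports the exclusion "Pregnant or lactating" in 4.2(m) and the immediate withdrawal on pregnancy required by 9.6.

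**The concern.** One protocol gives two definitions of the same status, and the looser one decides who has the safety test. The condition that no other medical reason explains the amenorrhea separates natural menopause from suppressed or interrupted cycles, and 8.3 leaves it out.

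The patients who fall between the definitions are plausible in this trial. Section 5.5 states that "patients who have been on gonadotropin-releasing hormone analogues for more than 90 days prior to study entry may continue while on study". A woman whose menses have been suppressed this way for 12 months or more fits the wording of 8.3, but 4.1(j) does not count her as postmenopausal, and she may still be fertile. If a site exempts her, pregnancy could go undetected at entry or during treatment, and the actions under 4.2(m) and 9.6 would not be triggered when they should be.

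The stake is patient safety at the margin. Nothing in the statistical analysis depends on it.

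**Working it through.** The plan states no figure on this point, so the check is mainly a comparison of texts.

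**Step 1: compare the definitions.**

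| | Protocol 4.1(j) notes | Protocol 8.3 |
|---|---|---|
| Term | postmenopausal | menopausal |
| Duration without menses | 12 months | at least 12 consecutive months |
| Condition on cause | no other medical cause | none |
| Used for | contraception criterion | exemption from pregnancy testing |

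Let A be the women amenorrheic for at least 12 months, and B the members of A with no other medical cause. Section 4.1(j) describes B and 8.3 exempts A. B is contained in A. The difference, A without B, is the women whose amenorrhea has another medical cause.

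**Step 2: narrow the difference to those affected.**
- Women after hysterectomy or bilateral oophorectomy have another medical cause, but 8.3 exempts them in their own right, and properly so.
- Women amenorrheic for less than 12 months are outside both definitions. A GnRH analogue used for just over 90 days before entry does not meet 8.3 on that basis alone.
- What remains is women with uterus and ovaries intact and at least 12 months of amenorrhea from a non-surgical medical cause.

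**Step 3: look for text that closes the gap.** Section 8.3 does not refer to 4.1. The pregnancy-test row of Table 4 has no footnote with the condition. Neither document defines childbearing potential in a way that settles who is tested. The recorded reason for exemption could simply be amenorrhea of 12 months or more, because 8.3 asks for no check of its cause.

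**Step 4: count the tests at stake per affected woman.** The inputs are the Table 4 schedule and assumed treatment durations of *w* weeks.

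Tests = 1 (screening) + floor(7*w*/28) + 1 (End of Treatment), less 1 if the last 28-day test coincides with End of Treatment.

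| Assumed weeks | Calculation | Tests | If the last two coincide |
|---|---|---|---|
| 12 | 1 + 3 + 1 | 5 | 4 |
| 24 | 1 + 6 + 1 | 8 | 7 |
| 48 | 1 + 12 + 1 | 14 | 13 |
| 60 | 1 + 15 + 1 | 17 | 16 |

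The count has no ceiling, because dosing continues "once weekly until patients meet one or more protocol-specific treatment discontinuation criteria". These are numbers of tests and do not measure risk.

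**Step 5: consider what else remains in place.** The contraception criterion, "Willingness of men and women of reproductive potential to observe conventional and effective birth control for the duration of treatment", would reasonably be taken to cover her, although the listed methods are only recommended. Physical examinations and scans continue, but neither replaces a pregnancy test. Scheduled scans are also less frequent: 6 weeks apart to Week 24, 8 weeks to Week 48 and 12 weeks after that, against 4 weeks between pregnancy tests.

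**The case against.** The strongest case on the other side is that a normal reading of the whole protocol resolves the point.

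- The first sentence of 8.3 requires testing of every woman of childbearing potential, and the 4.1(j) notes use that same term directly after defining postmenopausal.
- The Synopsis, under the birth-control criterion, sends the reader to 4.1 for reproductive-status detail.
- SAP 6.2.3 plans to summarize childbearing potential for women, so that status is treated as baseline data apart from the exemption reason.
- The two definitions serve different purposes, and failing the 4.1(j) definition does not by itself mean a woman must be tested. A woman after hysterectomy shows this.
- A woman with drug-suppressed cycles is not menopausal in the ordinary sense of the word.
- No such patient is shown to have enrolled, and the SAP (6.3 and 8) records the sponsor's decision to end the study before full enrollment.

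Much of this stands as mitigation. A careful site would test her, and the practical reach is small. It does not remove the inconsistency. The Synopsis reference and SAP 6.2.3 do not mention 8.3 and do not define childbearing potential. The exemption sentence carries its own definition, and a coordinator following that sentence would leave her untested. The hysterectomy example does not help, because 8.3 names that group separately.

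The early end of the study limits the value of a fix but does not clearly remove it. The documents do not say that all dosing has stopped. Appendix B foresees continued Australian enrollment, up to 16 participants, if global recruitment ceases for reasons other than futility or safety. The reason for ending is not given in enough detail to tell whether that applies.

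**Conclusion.** The concern holds at low severity. Section 8.3 exempts a wider group than 4.1(j) recognizes as postmenopausal, and no other text corrects it. Whether tests are actually lost depends on two things the documents do not settle: that such a woman is screened or treated, and that her site applies 8.3 on its own. Under those conditions every scheduled pregnancy test for her could be omitted.

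That she may still be fertile is an assumption about the individual woman. The treatment durations behind the test counts are also assumed. No endpoint, analysis population, sample size or power statement is affected.

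**What to change.** In 8.3, add to the menopausal definition the closing condition of the 4.1(j) note, so that both sections require 12 months without menses and no other medical explanation. Replacing the parenthesis in 8.3 with a cross-reference to the 4.1(j) note would do equally well. The separate exemptions for hysterectomy and bilateral oophorectomy stay as they are.

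The change is one phrase. Under 11.8 it needs a written amendment with IRB/EC approval, so it is best carried in another amendment if one is planned. The running cost is the tests that would otherwise be skipped: at most 5, 8, 14 or 17 per affected woman over an assumed 12, 24, 48 or 60 weeks, and more with longer treatment. It is worth making only while patients are still being screened or treated.
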